### Project Summary

Cervical myelopathy is commonly associated with degenerative spinal disease. Dysfunction of the autonomic nervous system is also evident in many cases of cervical myelopathy.

Autonomic dysfunction may result in haemodynamic instability and hypotension under anaesthesia. It is important to maintain adequate mean arterial pressure in order to perfuse the spinal cord and prevent cord ischemia. Heart rate variability, the physiological variations of the differences between heart beats, has been used to diagnose autonomic dysfunction. In patients with cervical myelopathy it may enable the anaesthetist to predict hypotension thereby allowing for early treatment and prevention of spinal cord ischemia.

## Background

Cervical myelopathy is commonly associated with degenerative spinal disease. It is a common cause of spinal cord dysfunction in the aging population. The predominant pathology seen in these patients is spondylosis which includes degeneration of joints, discs and ligaments. (1). Spinal cord ischemia may also contribute to these pathological processes but the exact mechanism remains unclear. Magnetic resonance imaging may reveal disc herniation, osteophytic narrowing of the spinal canal and hypertrophic changes to the ligamentum flavum (2). Patients may present with a wide range of symptoms ranging from neck pain and decreases in dexterity in mild cases to sphincter dysfunction and complete loss of motor function in severe cases (3). Dysfunction of the autonomic nervous system is also evident in many cases of cervical myelopathy (4). In many of these patients, the spinal cord is at risk of ischemia due to decreased blood flow as a result of compressive lesions. Any further reduction in spinal cord blood flow may not be well tolerated. Mean arterial pressure (MAP) is one of the important factors that determine the adequacy of perfusion to the spinal cord and hypotension has been shown to be associated with poor outcome in patients with spinal cord injury.

Autonomic nervous system dysfunction is often seen in patients with acute spinal cord injury. (5). A recent study has shown autonomic nervous system involvement in up to 50% of patients with compressive cervical myelopathy (4). The autonomic nervous system (ANS) is responsible for the normal regulation of visceral organ function including the cardiovascular system. They are the primary regulator of heart rate and blood pressure.

Surgical treatment of cervical myelopathy may involve anterior and/or posterior decompression of spinal cord with or without instrumented fusion. The main purpose of the surgery is to prevent further deterioration of spinal cord function. Patients with cervical myelopathy often pose a significant challenge to the anesthesiologists. In addition to challenges with airway management and patient positioning, the most important anesthetic consideration in these patients is to maintain the mean arterial blood pressure (MAP) >70 mmHg during the surgery.

Anesthetic induction may cause hypotension and this may be profound in some patients. Common causes of post-induction hypotension include vasodilatation, myocardial depression (6), hypovolemia and altered autonomic nervous system activity. Studies have shown that

patients with autonomic system dysfunction are more prone to anaesthesia induced hypotension. It has been shown that patients with autonomic dysfunction require increased vasopressor support to maintain blood pressure (7). Hence patients with cervical myelopathy, because of their associated autonomic system dysfunction, are possibly more prone to hypotension on induction of anaesthesia. This hypotension may put these patients at risk for spinal cord ischemia. Identifying patients at risk for hypotension can be useful to prevent hypotension and to prepare to treat hypotension sooner so that the risk of spinal cord ischemia can be minimized.

### Assessment of Autonomic Nervous System Function

Multiple methods have been used for the assessment of the ANS including, Valsalva test, isometric handgrip test, cold pressor test and active standing test. (8) Most of these tests are time consuming, labour intensive and are not easy to perform in the perioperative setting. Another method of assessment of ANS tone which affects cardiovascular function may be assessed by an analytical method called heart rate variability analysis. Guo et al. have shown that heart rate variability measurement is a simple useful alternative to conventional tests. (9).

### Heart Rate Variability (HRV)

Under normal physiological conditions the interval between successive cardiac cycles is not static but varies in response to several factors that place changing demands on the cardiovascular system. A decrease in the variability of the interval between cycles i.e. a decrease in heart rate variability has been shown to be associated with several pathological conditions that affect the autonomic nervous system (10).

Heart rate variability may be analysed according to either the frequency domain or the time domain. With regard to time domain analysis, the SDNN or Standard Deviation of normal R-R intervals is calculated during the period of ECG monitoring, the N-N interval being the interval between two successive normal beats. Using Fourier transformation, fluctuations in the frequency domain may also be analysed. The low frequency (LF) band (0.04-0.15 Hz) relates to sympathetic and parasympathetic modulation. The high frequency (HF) band (0.15-0.4Hz) largely reflects parasympathetic contribution. The ratio between low frequency and high frequency (LF: HF) is used to determine sympathetic-parasympathetic balance (11).

Heart rate variability may be analysed using standard hospital electrocardiographic equipment and the relevant software to perform the analysis. Power spectral analysis of the

electrocardiogram can be used to measure autonomic dysfunction. A short (5 minute) ECG recording can be analysed to provide several useful measurements of autonomic function. Therefore, heart rate variability analysis provides a non-invasive, bedside method of assessing the status of the autonomic nervous system that can be used in the perioperative setting without significant change to standard operating procedures.

### HRV as a predictor of Hypotension under Anesthesia

Haemodynamic stability under anaesthesia depends in a large part on the integrity of the autonomic pathways that feedback into cardiovascular regulatory centres and control variables like heart rate, contractility and vascular tone. As an indicator of autonomic function, heart rate variability may therefore have a role to play in predicting haemodynamic instability. Studies show that heart rate variability may be used as a predictor of haemodynamic fluctuations under anaesthesia. Hanss et al (12) have shown that the LF: HF ratio can be used to predict severe hypotension during spinal anaesthesia. In a study of patients under general anaesthesia Huang et al (13) showed that spectral analysis of heart rate variability could be used as a sensitive predictor of hypotension and that heart rate variability may be superior to traditional tests of autonomic function.

Heart rate variability is being increasingly used in the setting of general and regional anaesthesia as both a diagnostic and prognostic tool (8).

At present the incidence of decreased HRV in patients with cervical myelopathy is unknown as well as whether this is predictive of hypotension on induction of general anaesthesia. Therefore, the aim of our study is to determine the incidence of abnormalities in HRV in patients undergoing surgery for cervical myelopathy and to determine whether decreased heart rate variability is predictive of hypotension on induction in these patients.

### Hypothesis

We hypothesise that decreased HRV is common in patients undergoing surgery for cervical myelopathy and that decreased HRV is a predictor of hypotension on induction of general anaesthesia. We also hypothesise that there is a relationship between severity of myelopathy and degree of abnormalities in HRV.

### Significance of the study

Identifying patients at risk for hypotension can be useful to prevent hypotension and to prepare to treat hypotension sooner so that the risk of spinal cord ischemia can be minimized.

## Proposed methodology

### Study design

This is a single centre, prospective observational study.

### Trial Population

The study participants will be recruited from patients with cervical myelopathy presenting for cervical spine surgery at Toronto Western Hospital.

### Inclusion Criteria

Adults patients, aged 18 – 70 years with the history of cervical myelopathy, presenting for anterior or posterior cervical decompression and fusion.

### Exclusion Criteria

1. Patients with arrhythmias or absence of sinus rhythm
2. Diabetic patients
3. Degenerative neurological disease e.g. Parkinson's disease
4. Complete SCI
5. Inherited autonomic dysfunction

## Protocol

### 1. Standard perioperative management

Routine standard preparation of the patients will be carried out as per our institutional standard for all patients undergoing cervical spine surgery. All routine physiological monitoring (ECG, invasive arterial blood pressure, SPO2, end tidal CO2, temperature and depth of anaesthesia monitoring) will be performed. The induction of anaesthesia will be performed with propofol (2-5 mg/kg), fentanyl (3mcg/Kg) and rocuronium (0.6 mg/kg) for intubation of the patient's trachea once peripheral nerve stimulation shows no muscle twitches. After tracheal intubation, the lungs will be ventilated using volume-controlled mode to maintain PaCO2 between 33-35 mmHg. Anaesthesia will be maintained with total intravenous anaesthesia or balanced inhalational anaesthesia as per standard management. Hemodynamic management will target a MAP > 70 mmHg using standard inotropes and

vasopressors (phenylephrine and ephedrine). Prophylactic antibiotics (Cefazolin or Clindamycin), antiemetic (Ondansetron) and steroids (Dexamethasone) will be administered as per our routine practice. Intraoperative, 25 mcg bolus dose of fentanyl will be given for additional analgesia as indicated by clinical judgment. After the skin closure, anesthetic agents will be turned off and the neuromuscular blockade will be reversed with neostigmine 0.05 mg/kg and glycopyrrolate 0.01 mg/kg. Patient's trachea will be extubated after meeting the extubation criteria. Patients will be transferred to recovery room and standard postoperative care will be carried out. General care of the patients in the post-anesthetic recovery room will be as per our standard practice in terms of oxygen therapy, monitoring and assessment of neurological status, pain, nausea and vomiting and degree of sedation. Fentanyl 25 mcg i.v will be administered every 5 min to the maximum of 200 mcg to maintain a Numeric Pain Score (NRS) < 4 of 10. Morphine or hydromorphone will be used as additional analgesia after fentanyl. Nausea and vomiting will be treated with dimenhydrinate 25-50 mg i.v. Postoperative pain management will be provided with oral or parenteral opioid analgesia as per our standard of care

## 2. Study protocol

Before general anesthesia, following a 10 minute stabilization period with the patient lying supine and breathing at a rate of 12 – 15 breaths per minute, a 5 minute ECG recording will be obtained. ECG data will be downloaded onto a study laptop for later analysis using LabChart Software (ADInstruments, Colorado Springs, CO, USA) to determine HRV values (Total power, high frequency, low frequency and low frequency : high frequency ratios). Hemodynamic data (heart rate, systolic diastolic and mean blood pressure) and depth of anaesthesia (Entropy) will be collected from the preinduction period until skin incision at 1 minute intervals. The study will be complete after skin incision.

## Data Collection and Management

### Data Collection

The following data will be collected: patient demographics, surgical data including position technique, number of levels, duration, anaesthetic data including agents used, hemodynamic measurements from preinduction to surgical incision, Japanese Orthopaedic Association Score. The incidence of hypotension and the number of interventions required to keep mean arterial blood pressure above 70 mmHg will be recorded.

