## Analysis

The incidence of low HRV as indicated by a total power below the normal range of  $3466 \text{ ms}^2 \pm 1018 \text{ ms}^2$  will be determined as well as the incidence of hypotension. We will determine the correlation between low HRV, hypotension and the severity of myelopathy as determined by the Japanese Orthopaedic Association score. Non-parametric HRV within group data will be analysed with the Wilcoxon matched pairs test. Comparisons of non-parametric HRV data between groups will be performed using the Mann–Whitney test. Student t test will be used for parametric data.

Definitions:

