### Sample size

There is only one previous study that has looked at the autonomic dysfunction in patients with cervical myelopathy. They had a sample size of 30 patients and majority of patients had either moderate or severe myelopathy. Currently there is no data on the incidence of low HRV in patients with varying severities of cervical myelopathy. We plan to recruit around 100 patients with various degrees of cervical myelopathy for this study. Around 25 % of patients will be mild to moderate myelopathy and rest will be moderate to severe. Hence this sample size will provide us the useful information on the true incidence of autonomic dysfunction across different severities of myelopathy.

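### HRV is tested against hypotension and myelopathy severity without adjustment, and cardiovascular medication is neither recorded nor excluded, so the plan cannot show that HRV adds to routinely known factors.

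*Combined protocol and SAP*

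**What the plan says.** The design is stated as "This is a single centre, prospective observational study". The Hypothesis section has two association claims: that decreased HRV predicts hypotension on induction, and that HRV abnormality is related to the severity of myelopathy.

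For both, the Analysis section says "We will determine the correlation between low HRV, hypotension and the severity of myelopathy". It adds Wilcoxon, Mann–Whitney and t tests. No regression, stratification or covariate is named anywhere.

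Data Collection lists demographics, surgical data, "anaesthetic data including agents used, hemodynamic measurements from preinduction to surgical incision", the myelopathy score, the incidence of hypotension and the number of interventions. The Study protocol section adds minute-by-minute Entropy. The Blood Pressure definition adds treatments for hypotension and total vasopressor dose. Home medication and comorbidity appear in none of these.

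Some control is by restriction. The exclusions begin with "Patients with arrhythmias or absence of sinus rhythm" and go on to diabetes, degenerative neurological disease, complete spinal cord injury and inherited autonomic dysfunction. Cardiovascular drugs and hypertension are not among them. Eligible patients are "aged 18 – 70 years", and one total-power cut applies to all of them.

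**The concern.** The exclusions show that the plan wants to keep other causes of abnormal HRV out of the comparison. Beta-blockers, other antihypertensives and premedication can act on both heart rate and blood pressure, yet they are neither kept out nor written down. Age is not controlled either. It is presumably among the demographics, but has no role in the analysis.

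Two things are at stake. First, the Significance section wants to identify patients at risk of hypotension. For that purpose HRV is useful to the extent that it tells the anaesthetist something beyond age, baseline pressure and the drug chart, and an unadjusted test cannot show this. Second, the HRV-severity hypothesis concerns a relation between disease and autonomic function. If patients with worse myelopathy are also older or more often medicated, the crude correlation mixes these influences.

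Without a medication field, neither the investigators nor a reader could check either possibility.

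**Working it through.** **The plan's own figure.** The Sample size section says "We plan to recruit around 100 patients with various degrees of cervical myelopathy for this study". It gives no alpha, power, effect size, event rate or precision target, so the figure can be neither reproduced nor refuted. It is used below only as N = 100.

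**Could an unrecorded drug create an association?** All rates here are assumptions, because the documents give none:
- 20–40% of patients take such drugs.
- Low HRV occurs in 60–70% of users and 40% of non-users.
- Hypotension occurs in 35% of non-users, and the drug odds ratio for hypotension is 2–3.
- HRV has no effect within users or within non-users.

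Hypotension risk in users is p1 = OR·o/(1 + OR·o), with o = 0.35/0.65 = 0.5385. This gives p1 = 0.5185 for OR 2 and 0.6176 for OR 3. The risk in each HRV group is (share of users) × p1 + (share of non-users) × 0.35.

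Strongest corner (40% users, low HRV 70% v 40%, OR 3):
- Low-HRV fraction: 0.4 × 0.7 + 0.6 × 0.4 = 0.52.
- Users in the low group: 0.28/0.52 = 0.5385. Users in the normal group: 0.12/0.48 = 0.25.
- Risk, low group: 0.5385 × 0.6176 + 0.4615 × 0.35 = 0.494.
- Risk, normal group: 0.25 × 0.6176 + 0.75 × 0.35 = 0.417.
- Crude odds ratio: (0.4941/0.5059)/(0.4169/0.5831) = 1.37.

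The same steps for other cases:

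| Case | Risk, low HRV | Risk, normal HRV | Crude OR |
|---|---|---|---|
| 20% users, 60% v 40%, OR 2 | 0.396 | 0.374 | 1.10 |
| 40% users, 70% v 40%, OR 3 | 0.494 | 0.417 | 1.37 |
| Drug raises HRV: 20% users, 40% v 60%, OR 2 | 0.374 | 0.396 | 0.91 |
| Drug raises HRV: 40% users, 40% v 60%, OR 3 | 0.432 | 0.484 | 0.81 |

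**How large is that against sampling error?** In the strongest corner with N = 100, the standard error of the log odds ratio is √(1/25.7 + 1/26.3 + 1/20.0 + 1/28.0) = 0.40. A 95% interval therefore spans a factor of exp(1.96 × 0.40) ≈ 2.2 either way. The bias is ln 1.366/0.403 = 0.77 standard errors. The chance of a falsely significant positive result is about 4% at the mildest corner and 12% at the strongest, against 2.5% without confounding.

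A separate set of assumptions (50 patients per HRV group, 30% hypotension without the confounder) gives 1.15 for a confounder in 40% v 20% with OR 2, and 1.39 for 50% v 20% with OR 3. It reaches 1.99 only at 60% v 10% with OR 4, where the chance of a falsely significant positive result is about 39%.

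**How many terms can a model carry?** Taking 10 events per parameter as an assumed rule, hypotension in 20%, 30% or 50% of 100 patients supports 2, 3 or 5 parameters, HRV included. The first set of assumptions implies 38–46% hypotension, hence 38–46 events and 3 to 4 parameters.

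**Does induction dose belong in the model?** The propofol range in Standard perioperative management is 5/2 = 2.5-fold. The Study protocol section places the ECG recording before anaesthesia and its analysis later, so HRV values need not be known when the dose is chosen. Dose can then confound only through shared determinants such as age; otherwise it adds noise to the outcome. It is also unknown at the time a prediction would be made.

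**The case against.** The strongest reply is that the stated aim is prediction, and a marker can predict well even if its association runs partly through age or drugs. That stands. A reader might infer from the missing adjustment that the HRV-hypotension result would be invalid, or that it must be credited to autonomic dysfunction from myelopathy. The documents support neither. The Hypothesis and Analysis sections speak of prediction and correlation, and the Background offers the mechanism only as a possibility. What survives is narrower: added value over known factors cannot be shown. The prediction argument also does not answer the HRV-severity question.

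A reader might also infer that unrecorded induction dose is a major confounder. That is not supported, given the order of recording and dosing. In addition, the phrase about anaesthetic data is open-ended and could cover doses and premedication, fentanyl and rocuronium are set at single values per kilogram, and Entropy is recorded every minute. The accurate statement is that doses given are not specified. Home medication has no comparable opening in the list.

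Finally, the illustrated bias is small beside sampling error, its sign is unknown and every input is assumed. This also stands. It argues for a modest remedy rather than none. Adjustment for age and pre-induction pressure would remain possible afterwards from data already collected, but it would not be pre-specified, and medication would be missing.

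**Conclusion.** The point holds in limited form. It is established from the text that the association analyses are unadjusted and that cardiovascular medication is neither listed for collection nor excluded. It follows that the study, as planned, cannot show that HRV adds to age, baseline pressure and medication in predicting hypotension, and that its HRV-severity result is open to confounding by age and medication.

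The size and direction of any bias are not known. The range of 0.81 to 1.37 for the crude odds ratio with no true HRV effect rests wholly on assumed drug use, drug effects and event rates. It shows that bias in either direction is possible, including masking of a true effect, not that it will occur. The change is worth making because it is cheap. It does not call the study into question.

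**What to change.** - In Data Collection, add current beta-blocker or antihypertensive use (yes/no) and premedication. State that the induction doses actually given are recorded, for description only.
- In Analysis, pre-specify a logistic model for hypotension with log total power, age and antihypertensive use. Report it beside the crude estimate for the same HRV term, so that the two can be compared. Leave induction dose out.
- Add pre-induction mean arterial pressure, already collected, as a further term or sensitivity analysis only if the number of events allows. Autonomic dysfunction may itself affect this pressure, so adjusting for it could remove part of the association under study.
- State in advance how the model shrinks if events are few. By the rule above, three terms need about 30 events.
- Adjust the HRV-severity analysis for age and medication.
- If no adjusted analysis is done, label the results as unadjusted associations.

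No change to eligibility or treatment is needed. The cost is a few chart fields, one model and a slightly wider adjusted interval. For example, if 10% of the variation in HRV were explained by the covariates (an assumption), the interval on the log scale would widen by a factor of 1/√0.9 = 1.05. For an assumed 50% v 30% hypotension with 50 patients per group, power would fall from about 53% to 49%.

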## Data Management

An electronic data management system will be used. All data will be entered directly on the electronic system. Pre specified automated data entry checks will be performed on all entered data to prevent the entry of impossible values or the omission of key data fields. All study databases will be in the password protected UHN server. Any data containing participant identifying details will be stored separately and securely from study documents.

## Analysis

The incidence of low HRV as indicated by a total power below the normal range of  $3466 \text{ ms}^2 \pm 1018 \text{ ms}^2$  will be determined as well as the incidence of hypotension. We will determine the correlation between low HRV, hypotension and the severity of myelopathy as determined by the Japanese Orthopaedic Association score. Non-parametric HRV within group data will be analysed with the Wilcoxon matched pairs test. Comparisons of non-parametric HRV data between groups will be performed using the Mann–Whitney test. Student t test will be used for parametric data.

Definitions:

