### *1. Heart rate variability*

The Task Force of the European Society of Cardiology and the North American Society of Pacing and Electrophysiology has standardized guidelines for the measurement of heart rate variability (14). These recordings will be analysed and power spectrum densities will be calculated for total power (TP) which is a measure of heart rate variability. Low frequencies (LF), high frequencies (HF) and LF: HF ratio will also be analysed. Based on HRV values, two groups will be designated: group L (low HRV) and group N (normal HRV) based on the normal range for total power i.e.  $3466 \text{ ms}^2 \pm 1018 \text{ ms}^2$ .

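### For the aim of predicting hypotension from HRV, the Analysis section commits only to an unnamed correlation on dichotomised HRV and to tests between unidentified groups, with no effect estimate, discrimination measure or confidence interval

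*Combined protocol and SAP*

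**What the plan says.** **The aim.** The Background section on HRV as a predictor gives two aims: first the incidence of HRV abnormality, then to "determine whether decreased heart rate variability is predictive of hypotension on induction in these patients". The Hypothesis section repeats that "decreased HRV is a predictor of hypotension on induction of general anaesthesia". Significance of the study gives the use: "Identifying patients at risk for hypotension can be useful to prevent hypotension".

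**The analysis.** The Analysis section plans:
- the incidence of low HRV (total power below 3466 ± 1018 ms²) and the incidence of hypotension;
- a correlation: "We will determine the correlation between low HRV, hypotension and the severity of myelopathy as determined by the Japanese Orthopaedic Association score";
- between-group tests: "Comparisons of non-parametric HRV data between groups will be performed using the Mann–Whitney test", with Student's t test for parametric data;
- a within-group test: "Non-parametric HRV within group data will be analysed with the Wilcoxon matched pairs test".

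**The groups.** Under the HRV definition, "two groups will be designated: group L (low HRV) and group N (normal HRV"), split by the total-power range. The Blood Pressure definition makes three groups: none, hypotension and severe hypotension. Hypotension itself is a MAP below 70 mmHg for more than 1 minute.

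**The recording.** Under Study protocol, before general anaesthesia, "a 5 minute ECG recording will be obtained".

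**The concern.** The question is predictive, but the committed analysis is a test of association that is not fully specified. A significant correlation or p-value can show that HRV and hypotension are related. By itself it does not show how many patients who become hypotensive had low HRV, or how many who stayed normotensive would have been flagged. Those are the quantities a clinician needs to use HRV in the way the Significance section describes.

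Three choices are also left open: which coefficient is meant, whether hypotension enters as two categories or three, and which groups the Mann-Whitney and t tests compare. If these are settled after the data are seen, the results are harder to interpret.

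**Working it through.** There is no figure in the plan to reproduce. The documents give about 100 patients but no hypotension rate, share with low HRV, effect size, alpha or power. The rates and effects below are therefore assumptions, shown over ranges.

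**1. What a correlation alone conveys.** Let p be the share with low HRV, q the share hypotensive, and φ the correlation of the two yes/no variables. At n=100, φ is just significant at 1.96/√100 = 0.196. Then

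d = φ·√(p(1−p)) / √(q(1−q)); sensitivity = p + (1−q)d; specificity = 1 − (p − qd).

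For q=0.4 and p=0.5: d = 0.196 × 0.5/0.490 = 0.200, so sensitivity = 0.5 + 0.6 × 0.2 = 62% and specificity = 1 − (0.5 − 0.4 × 0.2) = 58%. The same φ gives these sensitivity/specificity pairs:

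| Hypotensive | 16% low HRV | 50% low HRV | 80% low HRV |
|---|---|---|---|
| 20% | 30/88% | 70/55% | 96/24% |
| 40% | 25/90% | 62/58% | 90/26% |
| 60% | 22/93% | 58/62% | 86/30% |

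So φ alone says little about predictive performance. But p and q are the two incidences that the Analysis section does plan to report. With φ, p and q all known, the formulas give one sensitivity and one specificity.

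**2. Why that depends on the coefficient.** Suppose a rank correlation is taken between low/normal HRV and the three blood-pressure groups. Let a1, a2 and a3 be the numbers with low HRV in groups 1 to 3, and r1 < r2 < r3 the mid-ranks. The low-HRV total fixes a1+a2+a3, and the coefficient fixes r1·a1 + r2·a2 + r3·a3. That is two equations for three unknowns. Sensitivity, (a2+a3) divided by the number hypotensive, can still vary as patients are traded between groups. It cannot be recovered.

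**3. The between-group tests.** HRV has two groups and blood pressure has three, and the Analysis section says only that groups are compared. Comparing total power between groups L and N would be circular, because total power defines them. If the intended comparison is hypotensive against not hypotensive, the Mann-Whitney U divided by n1·n0 is the AUC. The smallest significant AUC with 40 and 60 patients is 0.5 + 1.96·√(101/(12·40·60)) = 0.616. Its Hanley-McNeil 95% CI is 0.50-0.73, so a significant p-value is compatible with almost no discrimination.

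**4. Power lost by the split.** Simulation, n=100, HRV standard normal, OR 1.8 per SD (mean AUC about 0.66), two-sided 5%, 20,000 studies per row (Monte Carlo SE at most 0.35 points):

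| Hypotensive | Logistic, continuous | Mann-Whitney, continuous | Low/normal chi-square (16% / 50% / 80% low) |
|---|---|---|---|
| 20% | 59.8% | 58.9% | 41.2 / 43.6 / 22.6% |
| 40% | 76.8% | 75.7% | 46.8 / 60.3 / 43.9% |
| 60% | 77.0% | 75.8% | 38.5 / 59.8 / 50.5% |

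The absolute level depends strongly on the assumed OR. At 40% hypotensive, logistic power is about 23% at OR 1.3, 46% at 1.5 and 98% at 2.5 (3,000 studies each).

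**5. Precision of the proposed AUC.** With A=0.66, Q1 = A/(2−A) = 0.4925 and Q2 = 2A²/(1+A) = 0.5248,

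SE² = [A(1−A) + (n1−1)(Q1−A²) + (n0−1)(Q2−A²)]/(n1·n0).

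For 40/60, SE = 0.0567 and the half-width is 1.96 × 0.0567 = 0.11 (0.55-0.77). For 20/80, SE = 0.0723 and the half-width is 0.14 (0.52-0.80).

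**6. Wilcoxon matched pairs.** The test needs two HRV values per patient. The Study protocol section plans one recording, so there are no pairs.

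**The case against.** The strongest reply is that the planned results hold more than the correlation. The Analysis section also reports both incidences, and step 1 shows that with phi these fix sensitivity and specificity exactly. A reader might infer from the missing measures that the prediction aim cannot be answered at all. The documents do not support that: on the phi reading it can be. What survives is that the plan does not commit to phi, that a rank correlation over three blood-pressure groups would not allow the recovery, and that no interval is planned in either case.

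Second, the stated aim is whether HRV is predictive, and a test of association partly answers that. This is fair, but the use given in the Significance section needs the size of the predictive performance.

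Third, a Mann-Whitney test of continuous HRV by hypotension has almost the power of the logistic model (about 76% against 77%). True, so the power loss applies only where the low/normal split is used. That Mann-Whitney comparison is, however, only one reading of an unspecified grouping.

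Fourth, incidence is the first-named aim, and the Sample size section justifies about 100 patients on it. This stands: the change should be confined to the prediction aim.

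A reader might also infer that the tests are faulty because they are unadjusted. That is not the point. How well HRV on its own flags patients is an unadjusted question, and the analysis proposed here is unadjusted too.

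**Conclusion.** The point holds as a gap between a prediction aim and an analysis that commits to no estimate of predictive performance. That part rests on the text alone and needs no assumed input. The data remain usable, and the incidence aim is untouched.

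The size of the consequence rests on assumptions. One just-significant phi fits anything from 25/90% to 90/26% sensitivity/specificity at 40% hypotensive, unless it is read together with the low-HRV incidence. The split lowers power from about 76-77% to 44-60% at an assumed OR of 1.8 per SD and 40% hypotensive. The loss appears at 20% and 60% hypotensive as well, but the absolute figures should not be read as the study's power. The Wilcoxon test on HRV has no data to work on under the plan as written.

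**What to change.** In the Analysis section, for the prediction aim only:

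- Name as its main analysis a logistic model of any hypotension (the existing Blood Pressure definition) on continuous log total power. Report the OR per SD and the AUC, each with a 95% CI.
- Report sensitivity and specificity of the existing low-HRV cut-off, with 95% CIs.
- State that the Mann-Whitney test compares HRV between patients with and without hypotension.
- Keep the three blood-pressure groups as a secondary ordinal analysis, so that severity is not discarded.
- Delete the Wilcoxon matched-pairs test on HRV.

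The incidence analyses stay as they are.

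The cost is a few sentences and no new data. The downside is that the intervals will be wide at about 100 patients: for an AUC of 0.66, about ±0.11 if 40% are hypotensive and ±0.14 if 20% are. The small sample causes that imprecision, and the present plan would leave it unreported.
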